[figure not shown]
[figure not shown]
[figure not shown]

Boehringer
Ingelheim

Clinical Trial Protocol

Document Number:		c36371216-05
EudraCT No.	2021-005270-26	
BI Trial No.	0352-2159	
BI Investigational Medicinal Product	NA	
Title	Double-blind, randomized, parallel group, placebo controlled clinical trial to evaluate the effects of atomoxetine on impulsivity in behavioral laboratory tasks in adult ADHD patients	
Lay Title	A study to test different ways to measure the effect of atomoxetine on impulsive behavior in young adults with Attention Deficit Hyperactivity Disorder (ADHD)	
Clinical Phase	NA	
Clinical Trial Leader	 Phone: 	
Coordinating Investigator	 Phone: 	
Current Version and Date	Version: 4.0 28 Feb 2024	
Original Protocol Date	25 October 2021	Page 1 of 67

Proprietary confidential information. © 2024 Boehringer Ingelheim International GmbH or one or more of its affiliated companies. All rights reserved. This document may not - in full or in part - be passed on, reproduced, published or otherwise used without prior written permission.
		

CLINICAL TRIAL PROTOCOL SYNOPSIS

Company name	Boehringer Ingelheim
Original Protocol date	25 Oct 2021
Revision date	28 Feb 2024
BI trial number	0352-2159
Title of trial	Double-blind, randomized, parallel group, placebo controlled clinical trial to evaluate the effects of atomoxetine on impulsivity in behavioral laboratory tasks in adult ADHD patients
Coordinating Investigator	
Trial site(s)	Multicenter trial in approximately 5 clinical sites across Germany
Clinical phase	Not applicable
Trial rationale	To investigate the effects of impulsivity-reducing ADHD medication atomoxetine on impulsivity as measured by behavioral laboratory tasks in ADHD patients.
Trial objective(s)	Translational study to identify the best-suited impulsivity measures for use in future clinical trials, to investigate pharmacological modulation of impulsivity by atomoxetine after single dose and at steady-state, and to assess effect sizes and population variability.
Trial endpoints	
Primary endpoints:
 
Change from baseline after single dose and at steady state for:
 
Change from baseline in total score of Barratt Impulsiveness Questionnaire v.11 (BIS-11) after single dose (at day 1)Change from baseline in total score of Barratt Impulsiveness Questionnaire v.11 (BIS-11) at steady state (at day 14)Change from baseline in total score of S-UPPS-P Impulsive Behavior Scale after single dose (at day 1)Change from baseline in total score of S-UPPS-P Impulsive Behavior Scale at steady state (at day 14) 
Secondary endpoints:
 
Percentage of patients with (S)AEs
Trial design	Randomized, placebo-controlled, double-blind, parallel group trial.
Total number of patients randomised	80*
Number of patients per treatment group	40 per treatment arm <small>* Additional subjects may be entered to allow the sample size of 80 evaluable subjects who completed the study per protocol. Thus, the actual number of subjects entered may exceed 80, but will not exceed 96.</small>
Diagnosis	Adult Attention Deficit Hyperactivity Disorder (ADHD)

Main inclusion and exclusion criteria	Male and female subjects, age of 18-45 years; Diagnosis of ADHD according to DSM-5, currently undergoing diagnostic assessment and/or treatment for ADHD (registered with psychiatrist/ clinic/study site); Able and willing to discontinue the use of any psychotropic medications for treatment of ADHD symptoms, as well as of all relevant co-medication for comorbid conditions during the study; Subjects have a moderate symptom of ADHD with combined score of 4 or higher in Clinical Global Impression-ADHD-Severity (CGI-ADHD-S) at Screening; Hyperactivity/Impulsivity subscale of the ADHD check-list min 8 (at least moderate for impulsivity);
Test product(s)	Atomoxetine
dose	40 mg
mode of administration	Oral with 240 mL of water after an overnight fast of at least 10 h
Comparator product(s)	Placebo
dose	Not applicable
mode of administration	Oral with 240 mL of water after an overnight fast of at least 10 h
Duration of treatment	14 days with once daily doses
Statistical methods	For the single behavioral measures (primary endpoints), analysis of covariance (ANCOVA) will be used to compare means between groups. This will be done after single-dose and at steady state. Descriptive statistics will be calculated for all endpoints.

FLOW CHART

FLOW CHART (cont.)

Visit	Day	Planned Time [h:min]	time (actual day) [h:min] (Assumed dosing time is 8:00am, but the actual dosing time may differ for a particular subject)	Physical examination	███████████	Questionnaires ³	Laboratory/Urinalysis	PK sampling	C-SSRS	ECG, vital signs ⁶ (BP, PR)	Adverse events / Con. med
4	14		Pre-dose	X			X	X	X	X	X
		312:00	8:00 Drug administration								
		313:00	9:00 Breakfast								
		314:00	10:00		X	X		X ¹⁰			
		315:00	11:00					X ¹¹			
		316:00	12:00 Lunch Discharge from the site	X ¹³						X ⁹	
5	19-28	EOS ⁵	EOS	X			X		X	X	X

1. Screening to be performed within 28 days before drug administration; including subjects information (may be done the day before), informed consent, demographics including determination of the body weight, smoking and alcohol history, relevant medical history, concomitant medication, physical examination and review of vital signs/ECG/laboratory including pharmacogenomic, drug and virus screening, visual acuity test, C-SSRS, CGI-ADHD-S, and review of inclusion/exclusion criteria.
Patients may be familiarized with the behavioural test battery during the visit for screening.
2. ██████████
3. Questionnaires will consist of BIS-11 and S-Upps-P.
4. Subjects will be trained in the taking of the medication and the compliance app before receiving the dosages for the next timeframe. This will be performed once on day 1 (subjects will receive dosage for up to day 7) and once on day 8, when the dosage will be increased (subjects will receive dosage up to day 14).
5. End-of-study-examination (e.o.s.) to be performed at least 4 days after last drug administration. Including physical examination, vital signs/ECG/laboratory(except drug-screen); concomitant medication, C-SSRS, review of adverse events
6. All blood pressure measurements, as well as pulse rate will be measured after 5 minutes of rest in the supine position.
7. Urine Drug Test only
8. Telephone contact
9. Vital signs only
10. Shortly before starting the tests
11. Shortly after the tests/scales completion
12. Pre-dose
13. Formal assessment and confirmation of the patients fitness by investigator or designee

TABLE OF CONTENTS

TITLE PAGE	1
CLINICAL TRIAL PROTOCOL SYNOPSIS	2
FLOW CHART	4
TABLE OF CONTENTS	6
ABBREVIATIONS AND DEFINITIONS.....	10
1. INTRODUCTION.....	12
1.1 MEDICAL BACKGROUND	13
1.2 DRUG PROFILE	13
1.3 RATIONALE FOR PERFORMING THE TRIAL	14
1.4 BENEFIT - RISK ASSESSMENT.....	15
1.4.1 Benefits.....	15
1.4.2 Risks	15
1.4.3 Discussion.....	17

C-SSRS	Columbia Suicidal Severity Rating Scale
CTP	Clinical Trial Protocol
CYP	Cytochrome P450

DSM-5	Diagnostic and Statistical Manual of Mental Disorders
EC	Ethics Committee
ECG	Electrocardiogram
(e)COA	(electronic) Clinical Outcome Assessment
eCRF	Electronic Case Report Form
eDC	Electronic Data Capture
EoS	End of Study (corresponds with End of Trial)
EoT	End of Treatment
EudraCT	European Union Drug Regulating Authorities Clinical Trials Database
FOT	Fully outsourced trial
GCP	Good Clinical Practice
GMP	Good Manufacturing Practice

HA	Health Authority
IB	Investigator's Brochure
ICH	International Council on Harmonisation
IEC	Independent Ethics Committee

INN	International Non-Proprietary Name
IRB	Institutional Review Board
IRT	Interactive Response Technology
ISF	Investigator Site File
IUD	Intrauterine Device
IUS	Intrauterine Hormone-Releasing System
LPLT	Last patient last treatment
MedDRA	Medical Dictionary for Drug Regulatory Activities
p.o.	per os (oral)
PK	Pharmacokinetics
RA	Regulatory Authority
SAE	Serious Adverse Event
SC	Steering Committee
SOP	Standard Operating Procedure

S-UPPS-P	Short Urgency, Perseverance, Premeditation, and Sensation Seeking-Positive Urgency Impulsive Behavior Scale
SUSAR	Suspected Unexpected Serious Adverse Reactions
t _{max}	Timepoint of maximum plasma concentration
TMF	Trial Master File
WHO	World Health Organisation
WOCBP	Woman of childbearing potential

1. INTRODUCTION

Impulsivity, a neurocognitive endophenotype present in a broad range of psychiatric disorders, and defined as the tendency towards rash decisions without adequate forethought, often resulting in mistimed and premature actions [R20-4114].

[figure not shown]
Impulsivity can be broadly divided into motor and decisional subtypes reviewed below.

Motor impulsivity includes waiting impulsivity or premature anticipatory responding prior to a cue predicting reward and response inhibition or stopping inhibition of a prepotent response. Decisional impulsivity includes delay and probabilistic discounting of reward and reflection impulsivity - the tendency to make rapid decisions without adequate accumulation and consideration of the available evidence [R21-2496].

While there is relative consensus about the clinical significance of impulsivity, there has been less consensus regarding measurement of impulsivity. There have been two main broad ways to measure impulsivity in humans: questionnaires and behavioural laboratory measures [P15-02354]. Of the questionnaires, the Barratt Impulsiveness Scale (BIS) has been widely used, showing increased impulsivity in many different clinical populations [R06-1093; R15-1437]. The advantage of questionnaire measures of impulsivity is their ease of use and sensitivity across different patient populations.

S-UPPS-P Impulsive Behavior Scale is a 20-item self-report that assesses five subscales (urgency, premeditation, perseverance, sensation seeking, and positive urgency) that are used to measure five distinct dimensions of impulse behavior in adolescents and adults (ages 12 and older) [R19-3281]. It is designed to measure impulsivity across dimensions of the Four Factor Model of personality: Premeditation (lack of), Urgency, Sensation Seeking, Perseverance (lack of).

For the behavioral laboratory measures of impulsivity different assessments have been developed based on different behavioral definitions of impulsivity[R21-2496].

There is considerable evidence that disorders clinically associated with impulsivity show impairment on a variety of questionnaire and behavioral measures of impulsivity [R15-0969; R15-0953; R15-0954; R15-0957]. The key questions that will be addressed in this study include: (1) Do ADHD patients, with impulsivity as a core characteristic of the disorder, have a distinct behavioral profile based on questionnaire and behavioral laboratory measures before and after treatment with atomoxetine? (2) Are there specific measures that are reliable and sensitive measures of impulsivity which might be used across diagnoses? The answers to

these questions are of importance in the selection of outcome measures for treatment and Phase I/II assessments of potential pharmacotherapies for different disorders.

1.1 MEDICAL BACKGROUND

Although there have been several studies showing that medications can reduce impulsivity in clinical groups [[R15-3365](#); [R15-3366](#)], there has not been consistency in the impulsivity assessment battery across these studies. These studies are critical if impulsivity measures are to be used as outcome measures in clinical trials. This trial will take the first step in producing data on the reliability of the tests and scales in ADHD patients, with impulsivity as a core characteristic of the disorder. In addition, this study will produce information on the population variability and effect size after treatment for the different behavioral laboratory tasks in ADHD patients.

1.2 DRUG PROFILE

Atomoxetine is indicated for the treatment of Attention-Deficit/Hyperactivity Disorder (ADHD). The efficacy of Atomoxetine was established in several clinical trials and is approved for medical use since 2002 in the USA and 2006 in Germany for children, and since 2013 for adults. It has been shown to significantly reduce inattentive and hyperactive symptoms, and it has little known abuse potential. Atomoxetine's use can be abruptly stopped without significant discontinuation effects.

The initial therapeutic effects of atomoxetine usually take 2–4 weeks to become apparent. The maximum recommended total daily dose in children and adolescents over 70 kg and adults is 100 mg.

Mode of action

Atomoxetine is a highly selective norepinephrine reuptake inhibitor.

Key pharmacokinetic characteristics

Orally administered atomoxetine is rapidly and completely absorbed. First-pass metabolism by the liver is dependent on CYP2D6 activity, resulting in an absolute bioavailability of 63% for extensive metabolizers and 94% for poor metabolizers. Maximum plasma concentration is reached in 1–2 hours. The half-life of atomoxetine varies widely between individuals, with an average range of 4.5 to 19 hours. As atomoxetine is metabolized by CYP2D6, exposure may be increased 10-fold in CYP2D6 poor metabolizers. If taken with food, the maximum plasma concentration decreases by 10-40% and delays the t_{max} by 1 hour. Drugs affecting gastric pH have no effect on oral bioavailability. Atomoxetine is excreted primarily as 4-hydroxyatomoxetine-O-glucuronide, mainly in the urine.

Drug interactions

Atomoxetine is a substrate for CYP2D6. Concurrent treatment with a CYP2D6 inhibitor such as bupropion, fluoxetine, or paroxetine has been shown to increase plasma atomoxetine by

Proprietary confidential information © 2024 Boehringer Ingelheim International GmbH or one or more of its affiliated companies

100% or more, as well as increase *N*-desmethylatomoxetine levels and decrease plasma 4-hydroxyatomoxetine levels by a similar degree.

Atomoxetine has been found to directly inhibit hERG potassium currents with an IC_{50} of 6.3 μ M, which has the potential to cause arrhythmia. QT prolongation has been reported with atomoxetine at therapeutic doses and in overdose; it is suggested that atomoxetine not be used with other medications that may prolong the QT interval ([Appendix 10.2](#)), concomitantly with CYP2D6 inhibitors ([Appendix 10.1](#)) and caution to be used in poor metabolizers.

Other notable drug interactions include:

- Antihypertensive agents, due to atomoxetine acting as an indirect sympathomimetic
- Indirect-acting sympathomimetics, such as pseudoephedrine, norepinephrine reuptake inhibitors, or MAOIs
- Direct-acting sympathomimetics, such as phenylephrine or other α_1 adrenoceptor agonists, including pressors such as dobutamine or isoprenaline and β_2 adrenoceptor agonists
- Highly plasma protein-bound drugs: atomoxetine has the potential to displace these drugs from plasma proteins which may potentiate their adverse or toxic effects. *In vitro*, atomoxetine does not affect the plasma protein binding of aspirin, desipramine, diazepam, paroxetine, phenytoin, or warfarin

Residual Effect Period

The Residual Effect Period (REP) of Atomoxetine is 4 days and is projected based on 5* longest $t_{1/2}$ of 19h. This is the period after the last dose with measurable drug levels and pharmacodynamic effects still likely to be present.

Clinical Data

Commonly reported side effects of atomoxetine include constipation, insomnia, decreased appetite, and xerostomia. Other side effects include dermatitis, dysmenorrhea, erectile dysfunction, dizziness, dyspepsia, ejaculatory disorder, urinary hesitancy, ejaculation failure, and diaphoresis.

For a more detailed description of the Atomoxetine profile, please refer to the Summary of Product Characteristics (SmPC) [[R21-3079](#)]. For more uncommon adverse effect and risks mitigation

1.3 RATIONALE FOR PERFORMING THE TRIAL

The overall goal of this project is to investigate the effects of impulsivity-reducing ADHD medication atomoxetine on impulsivity as measured by questionnaires and behavioural laboratory tasks in ADHD patients.

This study is needed to establish appropriate protocols for impulsivity tasks, if impulsivity measures are to be used as outcome measures in future clinical studies that will eventually lead to approval of new medications for the treatment of impulsivity, potentially across different diagnostic disorders.

1.4 BENEFIT - RISK ASSESSMENT

The overall safety profile of Atomoxetine is outlined in the current Summary of Product Characteristics (SmPC) [[R21-3079](#)].

1.4.1 Benefits

Participation in this clinical trial is without any therapeutic benefit for patients taking part in this trial. Their participation, however, is of major importance to investigate pharmacological modulation of impulsivity by atomoxetine after single dose and at steady-state, to define the best-suited waiting impulsivity task to be used in future therapeutic trials. Subjects are exposed to risks of study procedures and risks related to the exposure to the trial medication.

Potential benefits:

Subjects will undergo a free, thorough psychiatric screening consisting of questionnaires and other behavioral measures of impulsivity as noted in the [flow chart](#). Any clinically relevant diagnoses discovered during this screening will be discussed with subjects and they will be referred for treatment for these abnormalities. Additionally, if the study medication proves to be safe and effective, it can be considered by investigator for the patients treatment after the study.

1.4.2 Risks

Procedure-related risks

The use of an indwelling venous catheter or venepuncture for e.g. blood sampling may result in mild bruising and, in rare cases, in transient inflammation of the wall of the vein, or nerve injury, potentially resulting in paraesthesia, reduced sensibility, and/or pain for an indefinite period.

The total volume of blood withdrawn per patient during the entire study will not exceed 300 mL. This is less than the volume of a normal blood donation (500 mL). No health-related risk to patients is expected from withdrawal of this volume of blood.

Drug-related risks and safety measures

Participants will be closely monitored during the trial participation (including safety laboratory, AE monitoring, physical and neurological examinations) to ensure that worsening of pre-existing conditions or any newly occurring events are detected and any necessary actions taken according to stopping criteria (see section [3.3.4](#)).

Suicide related behaviour (suicide attempts and suicidal ideation) has been reported in patients treated with atomoxetine.

Risk mitigation:

In the interest of ensuring participant safety, trial participants will be proactively screened and monitored for SIB.

Atomoxetine can affect heart rate and blood pressure. Most patients taking atomoxetine experience a modest increase in heart rate (mean <10 bpm) and/or increase in blood pressure (mean <5 mm Hg).

Risk mitigation:

- Subjects with relevant findings in BP, PR or ECG at Screening, cardiovascular disorders, history of relevant hypertension or orthostatic hypotension, fainting spells or blackouts, use of drugs that might prolong the QT/QTc interval, marked (Section [3.3.3](#)), or subjects with additional risk factors for Torsade de Pointes arrhythmia (Section [3.3.3](#)) are excluded from trial participation.
- Heart rate and blood pressure be measured and recorded before treatment is started and, during treatment, after dose adjustment to detect possible clinically important increases.

Very rarely, spontaneous reports of liver injury, manifested by elevated hepatic enzymes and bilirubin with jaundice, have been reported.

Risk mitigation:

- Liver enzymes (ALT, AST) will be measured before, during and after dosing.
- Atomoxetine will be discontinued in patients with jaundice or laboratory evidence of liver injury.

Treatment emergent psychotic or manic symptoms, e.g., hallucinations, delusional thinking, mania or agitation in patients without a prior history of psychotic illness or mania can be caused by atomoxetine at usual doses. Additionally, there have been rare reports of anxiety and depression or depressed mood, very rare reports of tics, aggressive behaviour, hostility, or emotional lability.

Risk mitigation:

- Patients will be closely monitored for the appearance of any psychiatric symptoms.
- Atomoxetine will be discontinued.

Seizures are a potential risk with atomoxetine.

Risk mitigation:

- Patients with a history of seizure will be excluded from study participation.
- Atomoxetine will be discontinued in any patient developing a seizure.

Although uncommon, allergic reactions, including anaphylactic reactions, rash, angioneurotic oedema, and urticaria, have been reported in patients taking atomoxetine.

Risk mitigation:

- Patients will be in-house at the trial site under close medical observation 4 hours after first drug administration.
- Patients with a history of severe allergic reactions or known allergy to atomoxetine will be excluded from the trial participation.

Atomoxetine has a minor influence on the ability to drive and use machines. Atomoxetine has been associated with increased rates of fatigue, somnolence, and dizziness relative to placebo in paediatric and adult patients.

Risk mitigation:

- Patients will be advised to use caution when driving a car or operating hazardous machinery until they are reasonably certain that their performance is not affected by atomoxetine.

For atomoxetine clinical data on exposed pregnancies and breastfeeding are limited.

Risk mitigation:

- Pregnant and lactating females will be excluded from the trial participation.
- Females of childbearing potential must also agree to use an acceptable method of contraception during the study participation up to until EOT.
- Exclusionary pregnancy testing will be performed at screening, and regularly during the study.

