4.2.2 Restrictions

4.2.2.1 Restrictions regarding concomitant treatment

Following medications are prohibited during the treatment period:

- All psychotropic medications, concomitant use of CYP2D6 inhibitors, sympathomimetics, Monoamine Oxidase Inhibitors (MAOI) should not be taken for two weeks before, during and 2 weeks after treatment with Atomoxetine, and at least 5 half-lives before base-line visit;

Proprietary confidential information © 2024 Boehringer Ingelheim International GmbH or one or more of its affiliated companies

- Antihypertensive Drugs, Pressor Agents (e.g., dopamine, dobutamine), beta 2 agonists or other drugs that increase/decrease blood pressure should be used cautiously because of possible effects on blood pressure and heart rate;
- Use of alternative or traditional medicines (e.g. Chinese traditional medicine, herbal medication, St. John's Wort, Ayurveda medications, etc.).

Occasional (single dose) concomitant use of benzodiazepines and non-benzodiazepine hypnotics are allowed during study at a dose equivalent to ≤ 1.0 mg of lorazepam per day, for the management of AEs (e.g. anxiety and/or insomnia). Such drugs should be stopped immediately after the AE is resolved and should be avoided within approx. 48 hours before planned impulsivity testing.

Stable therapy with SSRI might be continued with caution as judged by investigator (except for Paroxetine and Fluoxetine which are inhibitors of CYP2D6). If patient receiving current treatment with SSRI, the dose must have been stable for a minimum of 2 months prior to screening and when possible maintained at a lower range.

In case of AEs, any treatment deemed necessary per the clinical judgment of investigator for the management of AEs considering patient safety is allowed.

Investigators are encouraged to adhere to the restrictions listed in the [Appendix 10.2](#) or contact the sponsor or sponsor's medical representative.

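### Protocol 1.4.2 says users of drugs that may prolong QT/QTc are excluded, but the eligibility and co-medication rules leave this largely to the investigator's judgement

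*Protocol*

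**What the plan says.** Protocol 1.4.2, as mitigation for cardiovascular risk, lists groups of subjects who "are excluded from trial participation"; one is defined by "use of drugs that might prolong the QT/QTc interval". Section 1.2 gives the reason: because QT prolongation has been reported with atomoxetine, "it is suggested that atomoxetine not be used with other medications that may prolong the QT interval", with a reference to Appendix 10.2.

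The operative rules are in three places.

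- **3.3.3, exclusions.** Exclusion 7 concerns a prolonged QT/QTc or another relevant ECG finding. Exclusion 8 concerns other Torsade risk factors; its examples are not drugs. Exclusion 16 removes patients who must or wish to stay on restricted medication, with a pointer to 4.2.2.1, or on any drug thought likely to compromise safe conduct.
- **3.3.2, inclusion 4.** Patients must be able and willing to stop relevant co-medication; 4.2.2.1 and Appendix 10.2 are cited for reference.
- **4.2.2.1, co-medication.** The firm rule is "All psychotropic medications, concomitant use of CYP2D6 inhibitors, sympathomimetics, Monoamine Oxidase Inhibitors (MAOI) should not be taken for two weeks before", during and after treatment. Its exception is "Stable therapy with SSRI might be continued with caution as judged by investigator (except for Paroxetine and Fluoxetine which are inhibitors of CYP2D6"; for these patients "the dose must have been stable for a minimum of 2 months prior to screening and when possible maintained at a lower range". Further, "beta 2 agonists or other drugs that increase/decrease blood pressure should be used cautiously". On the QT list the wording is "Investigators are encouraged to adhere to the restrictions listed in the" Appendix 10.2, or to contact the sponsor.

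**The concern.** A safety section states a categorical exclusion, while the rules that sites apply at screening express it as encouragement and discretion. A site could follow 3.3.2, 3.3.3 and 4.2.2.1 correctly and enrol a patient whom 1.4.2 says is kept out. Two sites could also decide the same case differently.

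The clearest case is a patient on stable citalopram or escitalopram. The footnote to 3.3.3 admits major depressive disorder and generalized anxiety disorder in remission, so maintenance SSRI use is plausible. The mitigation in 1.4.2, read literally, excludes that patient; 4.2.2.1, read literally, admits the patient at the investigator's discretion.

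What is at stake is arrhythmia risk in a trial that offers participants no therapeutic benefit (1.4.1) and starts at 80 mg on Day 1, where the approved posology starts at 40 mg (4.1.2).

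**Working it through.** The plan gives no figure on this point, so the check sets the texts side by side and then counts entries.

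**Step 1: how each hazard in 1.2 is carried through.** One sentence in 1.2 names three.

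| Hazard in 1.2 | Operative rule |
|---|---|
| CYP2D6 inhibitors | Prohibited in 4.2.2.1, listed in Appendix 10.1 |
| CYP2D6 poor metabolizers | Exclusion 18, with genotyping before inclusion (5.6.2) |
| QT-prolonging drugs | No criterion in 3.3.3; adherence to Appendix 10.2 encouraged in 4.2.2.1 |

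Only the third lacks a binding rule.

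**Step 2: does exclusion 16 or inclusion 4 close the gap?** Exclusion 16 takes its content from 4.2.2.1. That section uses the word restrictions for Appendix 10.2, so a reader can argue that those drugs are restricted. But the title describing restricted co-medication belongs to Appendix 10.1. Section 4.2.2.1 also covers drugs that may be used with caution, so appearing there does not by itself mean exclusion. The safe-conduct limb of exclusion 16 is discretionary. Inclusion 4 cites Appendix 10.2 but does not define which co-medication is relevant, and it does not override the SSRI allowance.

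**Step 3: how much of Appendix 10.2 do firm drug rules reach?** Named drugs are counted; class headings and beta 2 agonists are left out.

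- Psychotropic: typical antipsychotics 3 + atypical antipsychotics 3 + SSRIs 2 + SNRI 1 + tricyclics 4 = 13.
- Non-psychotropic: class IA 4 + class III 3 + antibiotics 6 + other agents 9 = 22.
- Total: 13 + 22 = 35.

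| Route | Drugs reached |
|---|---|
| Psychotropic ban, less the two SSRIs | 13 − 2 = 11 |
| Non-psychotropics named in Appendix 10.1 (amiodarone, chloroquine, propafenone, quinidine) | 4 |
| Methadone, through the urine drug screen and exclusion 19 | 1 |
| **Reached** | **16** |
| Non-psychotropics left | 22 − 4 − 1 = 17 |
| Citalopram and escitalopram (by inference) | 2 |
| **Not firmly prohibited** | **19** |

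Check: 16 + 19 = 35. The 17 are four antiarrhythmics, six antibiotics and seven other agents (for example ketoconazole and hydroxychloroquine).

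**Step 4: ECG cover.** Flow Chart footnote 1 includes a screening ECG. SAP 4.11.3 lists ECGs at Visit 1, Day 8, Visit 4 and Visit 5, with none on Day 1. The Day 1 rows of the Flow Chart were not available to confirm this. At Visit 4 the ECG is pre-dose; the later check that day is vital signs only (footnote 9).

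**The case against.** The strongest reply is that the protocol already has a route to these drugs. Exclusion 16 points to a section that speaks of restrictions in Appendix 10.2, and inclusion 4 cites the same appendix. Under 6.2.1, restricted medication found at screening is stopped at least 2 weeks before baseline if the investigator judges that justified and safe. Under 3.3.4.1, a patient who needs a drug that interferes with the safety of the trial product stops treatment. This stands in part: a reader who infers that nothing in the operative text reaches QT-prolonging drugs goes too far. What remains is that each route depends on an undefined term or on judgement, whereas 1.4.2 states a fact.

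Second, 19 of 35 might be read as a measure of exposure. It is not. Exclusions 5, 7, 10, 13 and 24 would keep out most users of the 17 non-psychotropics through the underlying disease or the ECG. The CYP2D6 class ban may also catch inhibitors that Appendix 10.1 does not name.

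Third, the SSRI allowance is deliberate and conditioned on dose stability, a lower range where possible, and caution. For citalopram and escitalopram, Appendix 10.2 only recommends an ECG above 40 mg and 20 mg per day, and every patient has a screening ECG. That stands too: the documents do not show that allowing the two drugs is a mistake. The fault is that 1.4.2 does not state the exception.

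Finally, the sentence in 1.4.2 is broken just after the drug clause. A reader might infer that it points to a missing criterion in 3.3.3, but that pointer may belong to the QTc criterion (exclusion 7). The conclusion here rests on the stated exclusion, not on the pointer.

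**Conclusion.** The inconsistency is real and should be corrected. Section 1.4.2 states a categorical drug exclusion; 3.3.3 does not name it, 4.2.2.1 only encourages it, and the SSRI allowance cuts across it. The safeguards listed above, together with exclusion 8, reduce the risk but do not make the exclusion binding. By count, 19 of the 35 non-beta-2-agonist drugs in Appendix 10.2 are not firmly prohibited; the number of patients affected cannot be derived from the documents and is probably small.

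This rests on two readings: that the SSRI allowance covers citalopram and escitalopram, which 4.2.2.1 does not name, and that restricted in exclusion 16 does not automatically take in all of Appendix 10.2. If the sponsor intends the wider reading of exclusion 16, the gap narrows to unclear wording and the unstated exceptions. A reader might also infer a threat to the efficacy comparison; nothing in the documents supports one, and no effect on sample size or the primary analysis is claimed.

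**What to change.** 1. **4.2.2.1:** replace the encouragement with a prohibition of Appendix 10.2 drugs during treatment. Use the washout that already applies to other prohibited drugs: stopped at least 2 weeks (6.2.1) and at least 5 half-lives (4.2.2.1) before baseline. Exclusion 16 and the run-in rule then apply, patients who can wash out stay eligible, and drugs started after entry are covered. Keep the clause that allows necessary treatment of adverse events.
2. **4.2.2.1 and 1.4.2:** state the same exceptions in both. Beta 2 agonists stay under the existing caution rule; say so explicitly, because 1.2 groups them with direct-acting sympathomimetics and 4.2.2.1 bans sympathomimetics. Stable citalopram up to 40 mg or escitalopram up to 20 mg per day may continue with a normal screening QTc, unless the sponsor's medical team prefers to exclude both. These caps borrow the ECG thresholds in Appendix 10.2; the choice is medical.
3. **Exclusion 16:** cite Appendix 10.2 alongside 4.2.2.1.

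Simply deleting the drug clause from 1.4.2 would remove the contradiction but also the protection that 1.2 calls for.

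Cost: an amendment needing ethics committee and authority approval, as Amendment 3 did when it changed inclusion 1 and 4.2.2.1, and a slightly smaller eligible pool.
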